Experiment 1.2. To determine if miR-1 is necessary and sufficient to enhance adipocyte catecholamine sensitivity, Control exosomes will be transfected with miR-1 mimic (Control-plus) and RE exosomes with anti-miR-1 oligonucleotide (RE-minus). These modified exosomes will be incubated with 3T3-L1 adipocytes for 24 hr and then gene expression and catecholamine sensitivity measured as described in the SOP section.

Experiment 1.3. Based on our preliminary data, we hypothesize that RE-induced exosomal miR-1 is repressing expression of AP-2 α , a negative regulator of C/EBP α . To determine if AP-2 α is a target gene of miR-1 we will generate a luciferase reporter gene harboring the 3'-UTR of AP-2 α . We will assess the ability of miR-1 to

repress reporter gene expression; if so, then we will repeat the experiment with a mutant AP-2 α 3'-UTR reporter gene in which the predicted miR-1 binding site is mutated as previously described by us²⁴.

Experiment 1.4. Microarray analysis of epididymal adipose showed increased expression of genes involved in β -adrenergic signaling and lipolysis in response to RE that was blocked by GW4869 treatment (see Fig. 5). The purpose of this experiment is to use qPCR to confirm the microarray results and, importantly, determine if the observed changes in gene expression and effects of GW4869 treatment are the same in female mice (n=12/sex).

Statistical Analysis. A two-factor ANOVA (treatment X sex) will be used to determine if a significant interaction exists between factors for each dependent variable under consideration. If a significant interaction is detected, Scheffé post-hoc comparisons will be performed to identify the source of significance with $p \leq .05$.

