Expected Outcomes & Alternative Approaches. The preliminary data presented demonstrate that we have the necessary expertise to carry out the proposed experiments so we do not anticipate any technical issues. We expect to confirm the change in β -adrenergic signaling and lipolytic gene expression and the enhanced catecholamine sensitivity of adipocytes exposed to RE-induced exosomes. Moreover, we expect to confirm the basis for these exosome-mediated effects is the exosomal delivery of miR-1 to adipocytes. In particular, we expect to find that Control exosomes containing the miR-1 mimic will promote the same up-regulation in gene expression and enhanced catecholamine sensitivity as do RE exosomes. By contrast, we anticipate the introduction of an anti-miR-1 into RE exosomes will prevent the changes in gene expression and catecholamine sensitivity. What is more difficult to predict is whether or not AP-2 α is a bona fide target gene of miR-1. The miR-1 binding site within the 3'-UTR of the AP-2 α transcript does not conform to a "classical" miRNA binding site but the predicted thermodynamics of miR-1 binding of $\sim\Delta G = -20$ is relatively favorable so there is a reasonable chance we will see miR-1 regulation of AP-2 α expression.

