If we fail to demonstrate miR-1 regulation of AP-2 α , yet show that miR-1 is necessary for mediating the effects of RE exosomes on adipocytes, then we will explore the possibility that miR-1 targets a different repressor of C/EBP α such as Sp1, Shox2, CKIP-1 or G9a. We did not initially pursue these other repressors because the change in their respective mRNA expression was not consistent with regulation by miR-1 (see Fig. 7); however, there is the possibility that miR-1 is regulating one of these repressors at the level of translation and not mRNA stability. Finally, if we do not confirm our working model proposing enhanced catecholamine sensitivity, we will begin to explore the possible influence of RE-induced exosomes on the browning of adipose tissue. While our microarray analysis showed a striking increase in β -adrenergic signaling and lipolytic gene expression, we did detect increased expression of genes known to be involved in browning (Prdm16, PGC-1 α , UCP-1 and PPAR γ), although not as robust. This finding is not surprising given that C/EBP α is known to be involved in regulating the conversion of white adipose tissue into brown adipose tissue, as well as many other signaling pathways⁸⁸. Thus, we will pursue other mechanisms potentially regulated by C/EBP α if the results of proposed experiments do not support our working model.

Specific Aim 2: Determine if skeletal muscle fiber-derived exosomes promote adipocyte lipolysis through enhanced β -adrenergic signaling.

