Experiment 2.1. The purpose of this experiment is to confirm our preliminary results showing the down-regulation of miR-1 in myotubes in response to electrical stimulation and if there is a corresponding increase in muscle-specific exosomal miR-1 abundance. If this relationship is confirmed, we will next treat myotubes with GW4869 to block exosome release to determine if the down-regulation of myotube miR-1 expression with electrical stimulation is mediated by the exosomal export of miR-1 as shown in vivo (see Fig. 4). The expression/abundance of miR-1 will be determined by qPCR as described in the SOP section.

Experiment 2.2. Exosomes from non-stimulated and stimulated myotubes will be incubated with primary human adipocytes for 24 hr and then gene expression and catecholamine sensitivity measured as described in the SOP section. Adult-derived human adipocyte stem cells (ADHASC) were isolated previously from lipo-aspirates⁹¹. [name] lab has expanded and frozen ADHASC from 6 different individuals available for these experiments. We will begin with one line which has been already shown to differentiate very reproducibly and determine the effect of exosomes derived from stimulated and non-stimulated myotubes on gene expression and catecholamine sensitivity as described in the SOP section.

Experiment 2.3. The purpose of this experiment will be to determine if muscle-specific exosomal miR-1 is necessary and sufficient to enhance adipocyte catecholamine sensitivity. Non-stimulated exosomes will be transfected with miR-1 mimic (Control-plus) while stimulated exosomes will be transfected with anti-miR-1 oligonucleotide (Stim-minus). These modified exosomes will then be incubated with primary human adipocytes for 24 hr and gene expression and catecholamine sensitivity measured as described in the SOP section.

Statistical Analysis. A two-factor ANOVA (treatment X sex) will be used to determine if a significant interaction exists between factors for each dependent variable under consideration. If a significant interaction is detected, Scheffé post-hoc comparisons will be performed to identify the source of significance with $p \leq .05$.

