Following a brief rest period, subjects will perform two lower body RE tasks to failure (knee extension and leg press) with blood samples drawn pre- and immediately, 30, 60 and 90 minutes post-exercise. Biopsies of the vastus lateralis and abdominal subcutaneous adipose tissue will be obtained pre- and post-exercise (at approximately 60 and 90 min post, respectively; see graphic abstract in the Human Subjects section).

Experiment 3.1. Exosomal, muscle, and adipose miR-1 abundance will be quantified, as well as miR-1A/B primary transcripts in muscle and adipose by qPCR as described in the SOP section.

Experiment 3.2. Isolated exosomes from the 30 and 60 minute time points will be applied to differentiated ADHASC for 24 hr, and lipolysis *in vitro* and the β AR-3 pathway gene expression assessed as described in the SOP section. Pre-RE exosomes will be transfected with miR-1 mimic (Pre-plus) and 30 minute post-RE exosomes with anti-miR-1 oligonucleotide (Post-minus) and compared to mock transfected exosomes from those time points. These modified exosomes will be incubated with differentiated adipocytes to parallel Aim 1 mouse Experiments 1.1 and 1.2.

Methods.

Resistance exercise (RE). Following determination of each subject's one repetition max (1-RM, see Human Subjects section for detailed description), subjects will perform two exercises, knee extension and leg press at 80% of 1-RM, designed to work the quadriceps. Subjects will perform three sets of eight repetitions, with a 90-120 second rest between sets, with a fourth set performed to failure. RE will be performed on pneumatic resistance devices (Keiser Sports Health Equipment, Fresno, CA).

Muscle biopsy. A muscle biopsy will be obtained from the vastus lateralis at baseline and approximately 1 hr post-exercise under local anesthetic (1% Xylocaine HCl, 3cc). A 1/4 inch wide incision will be made and a sterile 5mm Berkstrom biopsy needle (Pelomi Industries, Denmark) inserted with suction to obtain a 100-200 mg muscle sample. [name], study physician and co-investigator on this project, has extensive experience with this procedure. It is well-tolerated and volunteers routinely provide multiple samples^{83,89,94-96}. Muscle is snap frozen in liquid nitrogen and stored at -80°C until RNA isolation.

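### Anti-miR-1 is listed only in exercise-side exosomes, so Experiments 1.2 and 2.3 cannot show that miR-1 is necessary for the exosome effect

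*Combined protocol and SAP*

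**What the plan says.** The stated purpose of Experiment 1.2 (Specific Aim 1) is "To determine if miR-1 is necessary and sufficient to enhance adipocyte catecholamine sensitivity". The modified arms are Control exosomes carrying the mimic (Control-plus) and "RE exosomes with anti-miR-1 oligonucleotide (RE-minus", to be read alongside the unmodified Control and RE exosomes of Experiment 1.1. Under Expected Outcomes & Alternative Approaches for Aim 1, "we anticipate the introduction of an anti-miR-1 into RE exosomes will prevent the changes in gene expression and catecholamine sensitivity". The same section makes a later choice, which C/EBPα repressor to pursue, depend on whether the team can "show that miR-1 is necessary for mediating the effects of RE exosomes on adipocytes".

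Experiment 2.3 (Specific Aim 2) repeats the necessity-and-sufficiency purpose. Non-stimulated exosomes get the mimic, and "stimulated exosomes will be transfected with anti-miR-1 oligonucleotide (Stim-minus".

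Experiment 3.2 (Specific Aim 3) has the same layout: "Pre-RE exosomes will be transfected with miR-1 mimic (Pre-plus) and 30 minute post-RE exosomes with anti-miR-1 oligonucleotide (Post-minus". These are compared with mock-transfected exosomes from the same time points. Experiment 3.2 does not itself speak of necessity.

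The SOP entry on exosome miRNA loss- and gain-of-function describes loading exosomes of either origin with either mimic or inhibitor. It does not say that all four combinations will be made. The analysis for Aims 1 and 2 is a two-factor ANOVA of treatment by sex with Scheffé comparisons. It has no exosome-source by anti-miR-1 term.

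**The concern.** Necessity is a statement about a difference: the RE-versus-Control gap should vanish once miR-1 is blocked. Measuring that gap under blockade needs anti-miR-1 in both kinds of exosome, and the experiments list it in one. Suppose anti-miR-1 lowers the adipocyte response whichever exosome carries it, for instance by blocking miR-1 already present before exercise, while the RE effect comes from other cargo. RE-minus would then drop towards Control and look like a prevented RE effect, although RE exosomes still outperform Control exosomes by the same amount.

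The other controls do not close this gap. Control-plus addresses sufficiency. Mock transfection, named only in Experiment 3.2, controls for the procedure and not for the oligonucleotide. A non-targeting oligonucleotide in the existing arms would still leave the Control-plus-inhibitor cell empty.

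At stake is the mechanistic conclusion of Aims 1 and 2 and the follow-up work that Aim 1 makes conditional on it. The sponsor's own GW4869 experiment (Preliminary Data) used the fuller design: the inhibitor was given before both sham and ablation surgery, and results were read against the respective sham group.

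**Working it through.** The documents give no effect size, SD or decision rule for these assays, so there is no planned figure to reproduce. The check has two parts: what the listed arms can estimate, and an illustration under stated assumptions.

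**1. Estimability (no assumed effect sizes).** Let S = 1 for RE exosomes, M = 1 for mimic and A = 1 for anti-miR-1, with mean response α + βS + μM + γA + δ(S×A). Here β is the RE effect, γ a general effect of anti-miR-1 and δ its RE-specific effect.

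| Arm | Mean | Listed? |
|---|---|---|
| Control | α | yes |
| RE | α + β | yes |
| Control-plus | α + μ | yes |
| RE-minus | α + β + γ + δ | yes |
| Control-minus | α + γ | no |

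- RE − RE-minus = −(γ + δ). Only the sum can be estimated. The design matrix has rank 4 for 5 parameters.
- Full necessity means that the RE effect remaining under anti-miR-1, RE-minus − Control-minus = β + δ, is zero. Without Control-minus it cannot be estimated.
- Adding Control-minus gives rank 5 of 5.

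The same algebra applies to Experiments 2.3 (stimulated or non-stimulated) and 3.2 (post- or pre-exercise).

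**2. Illustration.** Assumptions: unit SD, independent arms, RE effect d = 1.2, 1.5 or 2.0 SD, two-sided unadjusted t tests at 0.05, 40,000 runs per setting. Anti-miR-1 lowers every preparation equally (δ = 0), so the RE effect is fully retained. The pattern counted as prevented is: RE above Control, RE-minus below RE, and RE-minus not significantly different from Control. Ranges run over d.

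| General fall | n=6 per arm | n=10 | n=12 |
|---|---|---|---|
| half of d | 11-26% | 20-31% | 24-30% |
| equal to d | 29-76% | 56-93% | 67-95% |
| twice d | 12-30% | 1-24% | 0.3-19% |

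At 1.5 times d the rate is 35-61% for n=10 to 12. When miR-1 is truly and fully necessary (γ = 0, δ = −d), the rates match the middle row, because the three arms compared then have identical means.

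**3. With the added arm.** In the retained-effect scenario, RE-minus versus Control-minus is significant in 47-88% (n=6), 72-99% (n=10) and 80-100% (n=12) of runs. Under full necessity it is significant in that direction in about 2.5%.

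The interaction (RE − RE-minus) − (Control − Control-minus) has variance 4σ²/n, against 2σ²/n for RE − RE-minus, so its standard error is √2 times larger. The effect detectable with 80% power (normal approximation) is (1.96 + 0.84) × √(2/n) for RE versus RE-minus and (1.96 + 0.84) × √(4/n) for the interaction:

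- n=12: 1.14 and 1.62 SD
- n=6: 1.62 and 2.29 SD

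Under full necessity with d = 1.2 to 2.0, simulated interaction power is about 29-64% at n=6 and 53-92% at n=12. The 95% interval for the remaining RE effect has half-width t × √(2/n): 2.228 × 0.577 = 1.29 SD at n=6 and 2.074 × 0.408 = 0.85 SD at n=12.

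**The case against.** **The arm may be intended.** The SOP permits inhibitor in Control exosomes, so a reader might infer too much in saying that the protocol rules the arm out. That stands. What can be said is that no experiment, arm name or expected outcome includes it.

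**Necessity is not claimed in all three aims.** A reader might extend the criticism of the claim to Aim 3. The documents do not support that: Aim 3 asks whether miR-1 potentially mediates the crosstalk and seeks proof of principle. Experiment 3.2 shares the asymmetry, not the stated claim.

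**The high percentages are one case.** A reader might infer that most such experiments would mislead. The 29-76% and 67-95% arise when the general fall equals the RE effect, and only there do the rates match full necessity. The documents neither report a general fall nor give its size. The pattern counted as prevented is this review's rule, since the plan states none. With Scheffé comparisons across four arms, the equal-fall rates are 10-52% at n=6 and 26-88% at n=10. Arms may also share preparations, and pre- and post-exercise samples in Experiment 3.2 come from the same participants, so independence is a simplification. These points limit the illustration but leave the rank result untouched: for any size of fall, a general and a specific fall give the same expected data in the listed arms.

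**The added arm is not free of statistical cost.** This stands. The interaction needs twice the n per cell to detect the same effect.

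**Conclusion.** The concern holds for Experiments 1.2 and 2.3 as a gap between the listed arms and the claim of necessity. It applies to 3.2 only if necessity is to be claimed there. That a general anti-miR-1 fall and a specific block of the RE effect cannot be separated follows from the arms alone, at any sample size.

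How often this would mislead is unknown. Under the stated assumptions it ranges from about 0.3% to 95%, according to the size of the general fall, the RE effect and n. The documents do not show that anti-miR-1 has a general effect, only that the listed arms could not reveal one.

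**What to change.** In Experiments 1.2 and 2.3, add Control (non-stimulated) exosomes with anti-miR-1. In 3.2, add pre-RE exosomes with anti-miR-1, at least in a subset, if necessity is to be claimed there. State the full list of arms so that the SOP and the experiments agree. Report the RE effect remaining under anti-miR-1 (RE-minus versus Control-minus) with its confidence interval, together with the source by anti-miR-1 interaction. Since the interaction may be underpowered at the planned n, give weight to the interval: a non-significant remaining effect with a wide interval does not establish necessity. Control exosomes may carry some miR-1, so a fall in the new arm could be partly specific. A non-targeting oligonucleotide in both exosome sources would help interpretation.

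Cost: one more transfection per preparation, one more set of wells across the six conditions of the catecholamine sensitivity assay, and some of the control exosome material. The arm itself needs no further mice, participants or biopsies, but matching the precision of RE versus RE-minus for the interaction would take twice the n per cell. In 3.2 the extra assays could reach 80 participants, hence the subset.

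If the arm is not added, limit the conclusion in Aims 1 and 2 to saying that anti-miR-1 lowers the response to RE (stimulated) exosomes, and do not claim necessity. That costs nothing.

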Figure 10. Human exosomal miR-1 abundance following a bout of resistance exercise. Subjects performed a bout of resistance exercise (knee extension) to failure. Blood was collected pre- and post-exercise (0, 30, 60 and 90 minutes) followed by immediate isolation of exosomes from plasma and qPCR analysis of exosomal miR-1 abundance. Following resistance exercise, exosomal miR-1 abundance was trending higher after 30 and 60 minutes post-exercise, returning to baseline by 90 min. Data are presented as mean +/- SEM (n = 10).

used miR-1 as a readout of muscle-derived exosomes. To more rigorously test our working hypothesis that skeletal muscle-derived exosomes alter adipose metabolism, we have developed an *in vitro* model of RE using human myotubes. As shown in Fig. 9A-B, electrical stimulation of human myotubes appeared to increase myotube size compared to unstimulated myotubes and, importantly, resulted in a 5-fold increase in the abundance of miR-1 in exosomes isolated from the culture media (Fig. 9C). Moreover, there was a small decrease (9%) in myotube miR-1 expression with electrical stimulation (Fig. 9D). Although we were unable to run statistics because of insufficient “n” (n=2), the overall trend in myotube size and both exosomal and myotube miR-1 abundance follows the same general pattern shown in Fig. 1 for RE.

As an initial effort to test whether or not our working model translates into humans, we carried out a pilot study. Young, sedentary, adults (n=10, 5 females, 5 males) performed a bout of RE (knee extension) to failure. Blood was collected pre- and post-exercise (0, 30, 60 and 90 minutes). Exosomes were isolated from serum and miR-1 abundance quantified by qPCR. Thirty minutes

post-exercise there was a trend for an increase in exosomal miR-1 abundance. This result suggests that both mice and humans respond to RE in a similar manner by releasing miR-1 into the circulation through exosomes. Further, this pilot demonstrates we have the necessary expertise and infrastructure to successfully conduct the human RE study proposed in Aim 3.

Collectively, we have provided strong preliminary data to support a novel mechanism in which skeletal muscle, in response to RE, regulates adipose metabolism through the exosomal delivery of muscle-specific miR-1. Also, our preliminary data clearly demonstrate that we have both intellectual and technical expertise to successfully perform the proposed experiments.

APPROACH

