Rationale. Based on our miR-1 preliminary data we hypothesize that skeletal muscle-derived exosomes are responsible for promoting lipolysis in fat in response to RE; however, the lack of an accepted marker of skeletal muscle-specific exosomes prevents identification of the tissue source of serum exosomes. To address this limitation, and test our hypothesis, we have developed an in vitro model in which electrical stimulation of human primary myotubes promotes an increase in the abundance of exosomal miR-1 to a similar magnitude as that observed in vivo with synergist ablation (see Fig. 9). Using this model system, we will be able to specifically determine if skeletal muscle-derived exosomes are able to promote adipocyte lipolysis through miR-1 activation of β 3-AR expression by targeting AP-2 α expression. It will also enable detailed profiling of miRs in muscle-derived exosomes. An additional strength of this model system is that it will allow us to determine if what we have observed in mouse cells translates to human cells.

Design. Human primary myoblasts will be differentiated into myotubes as previously described by us^{89,90}. Through the Center for Muscle Biology, directed by [name], primary myoblasts have been isolated, expanded and characterized from vastus lateralis biopsies obtained from more than 100 healthy volunteers (<https://www.uky.edu/chs/muscle/bank>). We will use 10 distinct primary myoblast lines derived from both male

(n=5) and female (n=5) donors. After 1 week of differentiation, myotubes will be electrically stimulated for 8 hr (12V, 1Hz, 2ms) using an Ionoptix C-Pace Electrical Pulse Stimulator. A total of four 6-well plates can be stimulated at a time. Cells will be harvested after an additional 16 hr with no stimulation for total RNA isolation to compare with cells cultured for that time period (24 hr) with no stimulation. One well of stimulated and non-stimulated myotubes will be fixed, visualized with myosin heavy chain immunocytochemistry and imaged for measurement of myotube diameter using automated image analysis to quantify the hypertrophic response (see Fig. 9). At the time of cell harvest, media will also be collected from both stimulated and non-stimulated myotubes for the isolation of exosomes as described in the SOP section.

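### Aim 2's treatment-by-sex ANOVA has no donor term although the ten myoblast lines appear to be run both stimulated and unstimulated; secondarily, treatment comparisons in Aims 1 and 2 are tied to a sex interaction

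*Combined protocol and SAP*

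**What the plan says.** **Design (Specific Aim 2).** "We will use 10 distinct primary myoblast lines derived from both male" (n=5) and female (n=5) donors. Stimulated myotubes are harvested after 8 hours of stimulation and 16 hours of rest, to "compare with cells cultured for that time period (24 hr) with no stimulation". Media are collected from both kinds of culture for exosome isolation. Nothing assigns different lines to the two conditions, and nothing says outright that each line supplies both.

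**Analysis (Specific Aims 1 and 2).** Both Statistical Analysis paragraphs use the same wording: "A two-factor ANOVA (treatment X sex) will be used to determine if a significant interaction exists between factors". Scheffé comparisons follow only if that interaction is significant. No donor, block or repeated-measures term appears. Specific Aim 3 does specify a repeated-measures model.

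**What depends on the result.** Experiment 2.1 first looks for a fall in myotube miR-1 and a matching rise in exosomal miR-1, and then: "If this relationship is confirmed, we will next treat myotubes with GW4869 to block exosome release". In the Preliminary Data (n=2, too few for statistics), "there was a small decrease (9%) in myotube miR-1 expression with electrical stimulation", while stimulation "resulted in a 5-fold increase in the abundance of miR-1 in exosomes isolated from the culture media".

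**Other experiments.** Experiment 2.2 is read out in adipocytes, and for these the plan says: "We will begin with one line which has been already shown to differentiate very reproducibly". Experiments 1.2 and 2.3 list only the two modified exosome preparations each. Experiment 3.2, described as the human parallel to 1.1 and 1.2, does name mock-transfected comparators. Experiment 1.4 and the conditional step of 2.1 add GW4869 to the RE or stimulation comparison.

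**The concern.** Cultures from the same donor usually resemble each other. If each line is run both ways, a two-factor model treats 20 correlated values as independent. Stable donor differences then enter the error term for treatment and for treatment-by-sex, which makes those tests too strict. Sex varies only between donors, so it is tested against an error that is too small, which makes that test too lenient.

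The practical stake is a missed small effect. Experiment 2.1 proceeds to GW4869 only if the miR-1 relationship is confirmed, and one half of that relationship was a 9% change in the pilot. The treatment-by-sex interaction, the one test the plan names, also loses power.

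The second matter is separate. If the sexes respond alike, the only written route to pairwise comparisons is almost always closed. In experiments with more than two conditions, the statements that miR-1 is necessary and sufficient, or that GW4869 blocks the response, need specific comparisons that the analysis paragraphs do not name.

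**Working it through.** Aim 2 gives no effect size, SD, correlation or power, so there is no figure to reproduce. Everything below is an assumption-based range.

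**Inputs.** From the plan: 5 male and 5 female lines and a 0.05 level. Assumed: each line is run in both conditions, one value per line and condition, total SD 1, and a common within-donor correlation ρ of 0, 0.3, 0.5 or 0.7.

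**Expected mean squares, two conditions.**
- Without a donor term the error has 20 − 4 = 16 df. It pools between-donor variation (8 df, expectation 1+ρ) with within-donor variation (8 df, expectation 1−ρ). Its expectation is [8(1+ρ) + 8(1−ρ)]/16 = 1.
- Under the null, the numerators for treatment and interaction have expectation 1−ρ, and the numerator for sex has expectation 1+ρ. The first two ratios are therefore too small and the third too large.
- With a donor block, treatment and interaction are tested on the 8 within-donor df and sex on the 8 between-donor df. All three tests then hold 5%.
- Critical values are F(1,16) = 4.49 and F(1,8) = 5.32.

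For a treatment effect of d SD, the blocked test has noncentrality 5d²/(1−ρ). At d=1 and ρ=0.5 this is 5/0.5 = 10, which gives 79% power. The unblocked figures come from simulation.

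| | ρ=0 | 0.3 | 0.5 | 0.7 |
|---|---|---|---|---|
| Null rejection, treatment or interaction, no block | 5% | 2.3% | 1.0% | 0.2% |
| Null rejection, sex, no block | 5% | 8% | 11% | 13% |
| Power, treatment 1 SD, no block vs block | 56 vs 50% | 57 vs 65% | 58 vs 79% | 60 vs 95% |
| Power, treatment 2 SD, no block vs block | 99 vs 97% | >99 vs >99% | >99 vs >99% | >99 vs >99% |
| Power, interaction 1 SD, no block vs block | 18 vs 17% | 15 vs 22% | 12 vs 29% | 9 vs 44% |

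**The 9% pilot change.** Its SD is unknown. If the SD were 20, 10 or 5%, the effect would be 9/20 = 0.45, 9/10 = 0.9 or 9/5 = 1.8 SD. At ρ=0.5, power without vs with the block is then about 9 vs 24%, 47 vs 70% and 99 vs >99%. At ρ=0 the block loses instead: 16 vs 14%, 47 vs 43% and 97 vs 94%.

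**Secondary point, four conditions.** When the sexes respond alike, the treatment-by-sex test without a donor term is significant in 5, 1.6, 0.5 and 0.1% of runs at ρ = 0, 0.3, 0.5 and 0.7. With independent animals it is significant in 5%. The overall treatment F remains available: for condition means 0, d, d, 0 it has about 70% power at d=1 and 97 to 99% at d=1.5. It says that the conditions differ, not which ones. The stimulation-by-GW4869 contrast (only the stimulated, uninhibited condition raised by 1 SD) has 33, 31, 29 and 27% power without the block and 33, 44, 57 and 79% with it, at the same four correlations.

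**The case against.** **Scope.** These are mouse and cell-culture aims. Aim 3 already has a repeated-measures model and mock comparators, so no participant result is at stake. This stands and limits the weight of the point.

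**Pairing and size are not documented.** This also stands. If different lines were used for each condition, with one value per line, no donor term would be needed. The 9% change comes from n=2, and the SDs used above are illustrative.

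**A reader might infer that the omission creates false treatment findings.** The documents do not support that: with one value per line and condition and positive correlation, the treatment test is conservative. The reassurance has limits, however. The cultures are grown in 6-well plates. If replicate wells were analysed as separate units and donors differed in their response, the treatment test could become too liberal. The plan does not say how wells are handled.

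**A reader might infer that Aims 1 and 2 offer no treatment test, or leave the comparisons wholly open.** That goes too far. With two conditions the main-effect F is the treatment test. The Preliminary Data define the GW4869 comparison against each arm's own sham, and the Expected Outcomes sections of Aims 1 and 2 describe the intended patterns in words. Nor is the interaction test misplaced: sex is a stated question in Aim 1. Aim 2's expectation of no sex difference covers only miR-1 in myotubes and exosomes, not the adipocyte readouts. Experiments 1.2 and 2.3 have more than two conditions only if comparators are run, which is inferred.

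**Conclusion.** The main point holds, conditionally. If each line is run in both conditions, gives one value per condition and donor correlation is positive, the Aim 2 model does not fit its design. At correlations of 0.3 to 0.7 it gives up roughly 8 to 35 points of power for a 1 SD treatment effect (65−57 = 8; 95−60 = 35). It runs the named interaction test well below 5% and lets the sex test reach 8 to 13%, although the plan attaches no action to a sex main effect. Very large effects, as a true 5-fold exosomal change might be, are barely touched. The case is clearest for Experiment 2.1. In 2.2 and 2.3 the readout is adipocytes, starting from one recipient line, so myotube-donor correlation may be weaker.

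The secondary point is narrower. With more than two conditions, the comparisons that carry the conclusions are described in words but are not analysis contrasts, and the only written pairwise step depends on a sex interaction. Both points concern the laboratory aims only.

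**What to change.** **Aim 2.** State whether each line is run under every condition. If so, use a mixed (split-plot) model with donor as a random block, treatment within donor and sex between donors, after averaging replicate wells to one value per line and condition. Apply the same blocking in Experiments 2.2, 2.3 and 1.2 wherever the compared exosomes come from the same line or the same mouse.

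**Aims 1 and 2.** Do not make treatment comparisons conditional on the sex interaction.
- Experiment 1.4 and the GW4869 step of 2.1: test RE-by-GW4869 or stimulation-by-GW4869.
- Experiments 1.2 and 2.3: say whether unmodified or mock-transfected comparators are run, as in Experiment 3.2. If they are, test each modified preparation against its own comparator, with Holm adjustment for the two tests.
- Keep treatment-by-sex as a stated test.

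**Cost.** Wording only, unless comparator wells must be added. With two conditions and zero correlation, blocking costs about 5 points of power (56 vs 50% at 1 SD). It breaks even between correlations of 0.1 and 0.2 at that effect size. With four conditions the cost at zero correlation is about 1 point.
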